5.3 Toxicities and Dosing Delays

Any patient who receives treatment on this protocol will be evaluable for toxicity. Each patient will be assessed periodically for the development of any toxicity according to the Time and Events table (Section 7.1). Toxicity will be assessed according to the NCI Common Toxicity Criteria for Adverse Events (CTCAE), version 4.0. All severe adverse effects will be evaluated immediately by Drs. [name] or [name] and a decision will be made about stopping the study medication.

Toxicity and Dosing Delays	
Event	Action
Anaphylaxis	
Grade 1-2	N/A
Grades 3 – 4	Stop medication and consider removing subject from trial
Infusion site extravasation	
Grade 1-2	Hold until AE are tolerable and then restart medication.
Grade 3-4	Withhold until ≤ Grade 2
Pruritis	
Grade 1	Will provide topical intervention
Grade 2	Will provide oral intervention (e.g. diphenhydramine) and withhold until < Grade 2
Grade 3	Will administer oral corticosteroid or immunosuppressive therapy and withhold until < Grade 2
Any other unanticipated toxicity	
Grade 1-4	Management as per CTCAE version 4.0

5.4 Usual Care

All participants in both study arms will receive usual care for treatment and prevention of delirium, including but not limited to behavioral interventions, psychiatric consultation, and psychotropic medications at the recommendation of psychiatric consultants and discretion of the bone marrow transplant team. This proposed standardized management of delirium is detailed in the attached protocol (Appendix A), which provides a framework to minimize variability in the treatment of delirium among study participants.

5.5 Prohibited Medications/Treatments

There are no medications/treatments that would prohibit subjects from inclusion and continued assessment in this study.

5.6 Duration of Therapy

Treatment will continue for seven days or until:

- Unacceptable adverse event(s)
- Inter-current illness that prevents further administration of treatment
- Subject decides to withdraw from the study, **OR**

Decisions to remove a subject from the trial or discontinuation of treatment before planned study completion will be undertaken in conjunction with consultation from the study PI or Co-PI.

5.7 Duration of Follow Up

For determination of study endpoints, subjects will be followed for six months after receiving HSCT or until death. Patients removed from study treatment for unacceptable AEs will be followed for resolution or stabilization of the adverse event(s). All patients (including those withdrawn for AEs) will be followed after removal from study treatment as stipulated in the protocol.

5.8 Study Withdrawal

Patients will be removed from protocol therapy and the PI notified when any of the criteria listed in section 5.6 apply. The reason for discontinuation of the protocol therapy will be documented on the eCRF.

If a patient decides to withdraw from the study (and not just from protocol therapy) an effort will be made to complete and report study assessments as thoroughly as possible. At the time of withdrawal, Drs. [name] or [name] will attempt to establish as completely as possible the reason for the study withdrawal.

- The patient will be asked if they are willing to allow for the abstraction of relevant information from their medical record in order to meet the long-term follow up objectives outlined in the protocol.
- A complete final evaluation at the time of the patient's study withdrawal will be obtained with an explanation of why the patient is withdrawing from the study.
- If they are unwilling to come in for a final visit, then we will attempt to complete all assessments over the phone, through video conferencing, online, by email, or by mail that can be completed in this manner
- If the patient does not return for an end of study follow-up assessment, this will be documented in the eCRF.
- If the reason for removal of a patient from the study is an adverse event, the principal specific event will be recorded on the eCRF.

5.9 Study Questionnaires

5.9.1 Delirium Rating Scale (DRS)

The DRS is a 10-item, clinician-rated scale that rates the severity of delirium symptoms over a 24-hour period using all available information from the patient interview, mental status examination, medical history and tests, nursing observations, and family reports.³⁴ The maximum possible score is 32. A cut-off score of > 12 has been suggested to distinguish patients with delirium from patients with other neuropsychiatric disorders.^{34,35} Each assessment will require up to 10 minutes of the subject's time.

5.9.2 Functional Assessment of Cancer Therapy – Bone Marrow Transplant (FACT-BMT)

The FACT-BMT is a 47-item self-administered assessment which has been well validated in the literature and permits the measurement of HRQOL in bone marrow transplant patients.³⁶ It asks individuals to rate questions related to physical, social/family, emotional, and functional well-being on a 5-point Likert Scale (0, not at all to 4, very much). All participants who are enrolled in the trial will be evaluated pre-transplant and will have repeat assessment at one, three, and six month follow-up visits after transplant. If the subject exhibits difficulty in completing the assessment due to its length, the CRA will help the subject complete it by reading items and answer choices aloud. The FACT-BMT will take no greater than 15 minutes to complete.

5.9.3 Patient Reported Outcomes Measurement Information System – Depression (PROMIS-D)

The National Institute of Health's Patient-Reported Outcomes Measurement Information System (PROMIS) contains a depression bank.³⁷ We will use the PROMIS Depression 8a short form. Scores for all PROMIS measures are reported on the T-score metric in which the mean=50 and standard deviation (SD) = 10 are centered on the general population means. Higher scores represent greater degrees of mood symptoms. All participants who are enrolled in the trial will complete the self-administered assessment pre-transplant and will have repeat assessment at one, three, and six month follow-up visits after transplant. The PROMIS-D will take no greater than 5 minutes to complete.

5.9.4 Post Traumatic Stress Syndrome Scale 14 (PTSS-14)

The PTSS-14 is a 14-item self-administered assessment which has been well validated in the literature and permits the measurement of post-traumatic stress disorder (PTSD) symptoms.³⁸ It has been used in a variety of populations, including assessment following a period of delirium.³⁹ Questions are on a 7-point Likert-type Scale (1, never to 7, always) resulting in a total score between 14 and 98. Higher scores represent a more likely diagnosis of PTSD. All participants who are enrolled in the trial will be evaluated pre-transplant and will have repeat assessment at one, three, and six month follow-up visits after transplant. The PTSS-14 will take no greater than 10 minutes to complete.

5.9.5 Montreal Cognitive Assessment (MOCA)

The MOCA is a clinician administered tool which has been well validated in the literature, studied in a wide variety of patient populations, and permits assessment of cognitive impairment. It is measured on a 30-point scale with lower scores indicating greater impairment. Scores ≤ 25 are considered clinically significant. All participants who are enrolled in the trial will be evaluated at baseline and will have repeat assessment at one, three, and six month follow-up visits after transplant. The MOCA will take no greater than 10 minutes to complete.

5.9.6 Eastern Cooperative Oncology Group Performance Status (ECOG-PS)

The ECOG performance scale is one of the most widely used measures of functional status.⁴⁰ It has high reliability and validity and is frequently used to estimate prognosis and treatment eligibility in oncology clinical trials.⁴¹ ECOG performance status is scored on a 6-point scale with higher scores representing greater physical restriction due to illness. The ECOG-PS will take no greater than 2 minutes to complete.

6.0 DRUG INFORMATION

6.1 Thiamine Description and Management

6.1.1 Mechanism of Action

Thiamine combines with adenosine triphosphate (ATP) to form thiamine pyrophosphate, also known as cocarboxylase, a coenzyme. Its role in carbohydrate metabolism is the decarboxylation of pyruvic acid in the blood and α -ketoacids to acetaldehyde and carbon dioxide.

6.1.2 Indications

Thiamine hydrochloride injection is indicated for the treatment of Wernicke's encephalopathy, Wernicke-Korsakoff syndrome, thiamine deficiency, beriberi (wet or dry), peripheral neuritis in pregnancy, and with dextrose-containing IV fluids.

6.1.3 How Supplied

The drug will be obtained from commercial supply through UNC Pharmacy and UNC Investigational Drug Service (IDS).

Full prescribing information for (Thiamine) is available at:

http://editor.fresenius-kabi.us/Pis/Thiamine_Inj_45819E_May_08.pdf

6.1.4 Dosage and Administration:

Subjects in the intervention group will receive Thiamine 200 mg IV tid.

6.1.5 Storage and Stability:

Thiamine should be stored at room temperature (between 68° to 77° F).

6.1.6 Handling and Disposal: Local requirements for disposal of hazardous drugs will be followed.

Please see UNC policy on hazardous drugs:

<http://news.unchealthcare.org/empnews/att/2011/nov/admin0188/>.

6.1.7 Adverse Events Associated with Commercial Drug

In a study of 989 patients given a rapid IV push of 100 mg IV thiamine, the only identified side effects were immediate, transient burning (1.02%) and generalized pruritis (0.093%).²⁷ Anaphylaxis has been reported at a rate of one reaction per every 5 million ampules used.²⁸ The following have also been reported with unknown frequency: a feeling of warmth, weakness, sweating, nausea, restlessness, tightness of the throat, angioneurotic edema, cyanosis, pulmonary edema, and hemorrhage into the gastrointestinal tract. Parenteral doses of 100 to 500 mg singly have been administered without adverse effect.²⁹ A comprehensive list of adverse effects can be found at the following web address: http://editor.fresenius-kabi.us/Pis/Thiamine_Inj_45819E_May_08.pdf

7.0 EVALUATIONS AND ASSESSMENTS

7.1 Time and Events Table

	Baseline (Pre- Transplant)	Post-Transplant Day 1	Post-Transplant Days 2 – 30	F1 ^c	F2	F3
Informed Consent	•					
Group Assignment	•					
Demographic Data Form	•					
Cancer History Form	•					
Delirium Risk Factor Form	•	•	•			
Concurrent CNS Active Medication Tracking Form	•	•	•			
Baseline Labs ^a		•				
Thiamine Levels ^b		•	•			
FACT-BMT ^c	•			•	•	•
PROMIS-D ^c	•			•	•	•
PTSS-14 ^c	•			•	•	•
MOCA ^c	•			•	•	•
ECOG-PS ^c	•			•	•	•
DRS ^d	•	•	•			
Adverse Events Form		•	•			

- a. Complete Blood Count (CBC), Comprehensive Metabolic Panel (CMP), Magnesium (Mg), Phosphorus (Phos)
- b. Thiamine levels will be drawn on post-transplant day 1, 8 days post-transplant, 15 days post-transplant, 22 days post-transplant, and 29 days post-transplant.
- c. FACT-BMT, PROMIS-D, PTSS-14, MOCA, and ECOG-PS will be performed at baseline (pre-transplant) and at one (F1), three (F2), and six months (F3) after transplant.
- d. DRS will be performed at baseline, on post-transplant day 1, and three times weekly thereafter. If a participant is identified as having delirium, assessments will increase to daily until delirium resolves at which point frequency will resume at three times weekly. For participants who develop delirium during the inpatient phase, DRS will be performed at one (F1), three (F2), and six months (F3) after transplant.

7.2 Pre-Study (Baseline) Assessments

Patients scheduled for admission to the UNC Bone Marrow Transplant unit will be considered for enrollment in this trial. Prior to transplant, the clinical research assistant (CRA) will review the trial with the subject, obtain informed consent, and the subject will complete self-report assessments for depression (PROMIS-D), post-traumatic stress symptoms (PTSS-14), and HRQOL (FACT-BMT), as well as clinician-rated assessments of cognition (MOCA), functional status (ECOG-PS), and for delirium (DRS). See Appendices A – F. The CRA or investigators will also conduct a review of electronic medical records to obtain baseline information regarding delirium risk factors, the subject's cancer and cancer treatment, and demographic information.

7.3 Randomization

If the patient meets all inclusion/exclusion criteria, provides informed consent, and is not delirious ($DRS \leq 12$), the subjects will then be randomized in a 1:1 ratio to the intervention or control arms in a double-blind fashion such that the investigators, biostatistician, CRA(s), nursing staff, and subjects will not know which agent is being administered. The statistician of record will design a block randomization scheme, stratified by age (<65 or ≥ 65) and baseline cognitive function ($MOCA >25$ or ≤ 25), both well-known risk factors for delirium. This information will be provided to UNC Investigational Drug Services, who will manage the actual assignment of subjects to each arm using the randomization list designed by the statistician.

7.4 Post-Transplant Days 1 – 30 Assessments

Within two days of transplant, the subject will have a CBC, CMP, Mg level, Phos level, and Thiamine level drawn. The CRA(s) or investigators will perform the delirium assessment (DRS), and a brief history will be obtained to assess for any toxicity from therapy.

Over the course of 30 days following transplant (or discharge, whichever comes first), the subject will continue to have weekly thiamine levels drawn (at days 8, 15, 22, and 29 +/- one day). The CRA(s) or investigators will continue to assess for delirium, using the DRS, three times weekly. If a subject is determined to

have delirium, frequency of delirium assessments will increase to daily, Monday through Friday, as scheduling permits, until delirium resolves. The DRS assessments will not be performed if a patient becomes unevaluable due to an acute medical concern (e.g. intubation, sedation, etc.). The CRA(s) or investigators will continue to assess for any toxicity from therapy.

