2.2 Secondary Objectives

2.2.1 To compare delirium severity between recipients of high dose IV thiamine and placebo during hospitalization for allogeneic HSCT.

2.2.2 To compare delirium duration between recipients of high dose IV thiamine and placebo during hospitalization for allogeneic HSCT.

2.2.3 To determine if thiamine status is predictive of subsequent delirium onset.

2.2.4 To investigate the effects of high dose IV thiamine on long-term health-related quality of life (HRQOL), functional status, depression, post-traumatic stress symptoms, and cognitive functioning in patients who undergo HSCT.

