5.2 Treatment Dosage and Administration

Subjects in the intervention group will receive thiamine 200 mg IV tid for seven days beginning on the day after of transplant. Subjects in the control group will receive 100 mL (equivalent volume to intervention) normal saline IV tid for seven days beginning on the day after transplant. All investigators will be blinded to which patients are assigned to which arm of the study. Only the Investigational Drug Service (IDS) will be aware of which patients will be assigned to which arms. At any time, the PI, primary medical providers, or other emergency personnel may request unblinding of a subject’s randomized treatment from IDS. If there is an adverse reaction, subjects will be treated symptomatically and consideration will be given to stopping the medication, as outlined in Section 5.3.

REGIMEN DESCRIPTION				
Group	Agent	Dose	Route	Schedule
Intervention	Thiamine	200 mg Thiamine HCL solution in 100 mL infusion bag of 0.9% Sodium Chloride	IV over 30 minutes (50 ml/hr)	Post-transplant Days 1 – 7 three times daily

Control	Normal Saline	100 mL of 0.9%	IV over 30 minutes (50 ml/hr)	Post-transplant Days 1 – 7 three times daily
---------	---------------	----------------	-------------------------------	--

Prescribing Information

Full prescribing information for thiamine can be found at the following web address: http://editor.fresenius-kabi.us/Pis/Thiamine_Inj_45819E_May_08.pdf

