7.11 Assessment of Efficacy

In order to be considered evaluable for efficacy, patients must:

- receive all 7 days of the treatment; a patient must receive at least 17/21 (80%) thiamine doses
- have delirium assessed at least weekly until one of the following is met:
 1. The participant is found to be delirious (DRS>12)
 2. The participant is at least 30 days post-transplant
 3. The participant is discharged

If a patient is deemed not evaluable, they will be replaced by a new patient. However, if a patient develops delirium during the intervention, they will still

receive the full 7 day course, not be replaced, and included in the efficacy analysis.

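### The first thiamine level is not tied to the first infusion, and the only planned predictor for objective 2.2.3 is a post-treatment level analysed without regard to arm

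*Combined protocol and SAP*

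**What the plan says.** **Dosing.** Section 5.2 states: "Subjects in the intervention group will receive thiamine 200 mg IV tid for seven days beginning on the day after of transplant". The regimen table gives both groups the same timetable, "Post-transplant Days 1 – 7 three times daily". Section 7.11 confirms a total of 21 doses: "a patient must receive at least 17/21 (80%) thiamine doses".

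**First thiamine level.** Three current places give its timing:
- Section 1.1 (synopsis): the day after transplant.
- Section 7.1, footnote b: "Thiamine levels will be drawn on post-transplant day 1, 8 days post-transplant", with no window.
- Section 7.4: "Within two days of transplant, the subject will have a CBC, CMP, Mg level, Phos level, and Thiamine level drawn".

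None of them mentions the first infusion. The pre-transplant column of the Time and Events Table has no thiamine entry, and Section 7.2 lists no thiamine level among the baseline assessments.

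**Later levels.** Section 7.4 sets these "at days 8, 15, 22, and 29 +/- one day".

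**Use of the levels.** Objective 2.2.3 reads: "To determine if thiamine status is predictive of subsequent delirium onset". Sections 3.2.2 and 9.3 both take the level after the seven-day course as the predictor. Section 9.3 plans ROC curves and a search for a cutoff, and leaves out patients who become delirious before treatment ends. It does not say how arm enters the analysis.

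**The concern.** By the end of the seven-day course half the patients have been assigned IV thiamine and half saline, so the level at that point largely records who received what. If thiamine also lowers delirium, as the trial hypothesises, low levels and delirium will go together in the combined sample even if a patient's own thiamine status tells nothing further. A cutoff found that way could mainly separate the arms.

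A level taken before any study drug avoids this, because randomisation cannot have affected it. The trial already pays for a sample close to that moment but does not secure it. A first draw after dosing has begun is altered in the thiamine arm only, so the error would differ between arms. Section 1.5 says that the co-occurrence of deficiency and delirium in HSCT is unknown and offers the trial as a source of data on their timing, which makes a clean first level worth having.

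**Working it through.** **1. The plan's own figure.** No power or sample size is given for objective 2.2.3. The only such figure is for the primary endpoint (Section 9.2): 0.445 against 0.155, 30 evaluable per group, one-sided 0.05, 80% power. With pooled variance and no continuity correction:

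- mean proportion = (0.445 + 0.155)/2 = 0.30
- z = [0.29 × √30 − 1.645 × √(2 × 0.30 × 0.70)] / √(0.445 × 0.555 + 0.155 × 0.845) = (1.588 − 1.066)/0.615 = 0.85
- power = Φ(0.85) = 0.802

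The figure reproduces. It is not in question here; its two rates are borrowed in step 3.

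**2. Doses given before each permitted draw.** Three doses a day on days 1 to 7 make 21. Before a draw on day d, at least 3(d − 1) and at most 3d have been given, capped at 21.

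| Draw | Permitted by | Doses already given | Doses outstanding |
|---|---|---|---|
| Day 0 or earlier | 7.4, if its window runs both ways | 0 | 21 |
| Day 1 | 1.1, 7.1, 7.4 | 0 to 3 | 18 to 21 |
| Day 2 | 7.4 | 3 to 6 (14% to 29%) | 15 to 18 |
| Day 7 | 7.4 (day 8 less one) | 18 to 21 | 0 to 3 |
| Day 8 or 9 | 7.4 | 21 | 0 |

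A draw on day 1 before the first infusion satisfies all three sections. An on-schedule day 2 draw is always post-dose.

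**3. How far arm alone can produce a predictor.** Assumptions: equal arms; every thiamine patient's end-of-treatment level lies above every placebo patient's; the level has no predictive value within an arm; delirium rates are 0.445 (placebo) and 0.155 (thiamine).

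- Share of delirious patients on placebo: a = 0.445/(0.445 + 0.155) = 0.742
- Share of non-delirious patients on placebo: b = 0.555/(0.555 + 0.845) = 0.396
- ROC area for a low level = a(1 − b) + ½[ab + (1 − a)(1 − b)] = 0.5 + (a − b)/2 = 0.5 + 0.345/2 = 0.67

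An uninformative marker gives 0.50. The exclusion of early delirium in Section 9.3 need not change this. It removes cases only, so b is unchanged, and a is unchanged if the same share of cases is removed in each arm.

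**4. Events available.** At the planning rates, 30 × 0.445 ≈ 13 and 30 × 0.155 ≈ 5 delirious patients per arm. These are upper limits for the Section 9.3 analysis, which drops early cases.

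**The case against.** **The plan never proposes a pre-dose predictor.** True. The end-of-treatment level precedes the delirium that is counted, so the analysis can be run and answers a forward-looking question. The pre-dose analysis is an addition. The missing treatment of arm in the analysis already planned is a separate weakness, and it stands.

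**Contamination is only possible.** Also true. Two of the three sections say day 1, and an early draw that day is clean. A reader might infer that the trial has no baseline thiamine level. The documents support only that none is guaranteed.

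**A pre-dose level may come too early.** Section 1.2 cites a study in which every patient developed deficiency during the post-transplant stay, so a sample at its start may miss the deficiency of interest. In addition, if thiamine works it should weaken the link between first level and delirium in the treated arm, which a main effect for arm does not capture. Both points stand. They argue for a second predictor with an arm interaction, not for replacing the planned one.

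**Treated patients are not lost.** A reader might infer that only placebo patients are interpretable after treatment, so that a pre-dose level would double the usable sample. Nothing in the documents shows this. Treated patients' levels can be examined within arm or with adjustment, and no such gain is claimed here.

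**The day 7 draw is minor.** A reader might infer that sampling on the last dosing day undermines the planned predictor. At most 3 of 21 doses are outstanding, and the summary of Amendment 2 explains that the one-day window was added to catch patients discharged just before a draw. It has no bearing on whether a pre-treatment level exists.

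**Conclusion.** The point holds as an inexpensive improvement to one secondary objective. The primary endpoint and its power are untouched.

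Two things are established from the text: the sections disagree on when the first thiamine sample is due and none places it before the first infusion; and the sole planned predictor is measured after randomised treatment, with no mention of arm. The first means that a nominal day 1 level may follow 0 to 3 of 21 doses, or 3 to 6 on day 2, with study drug present in the thiamine arm only. The second means that the ROC curve and cutoff can partly reflect treatment assignment.

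The area of 0.67 is an illustration, not a forecast. It rests on complete separation of levels by arm and on the planning rates. Overlapping levels or a smaller treatment effect would bring it closer to 0.50. It shows only that a seemingly useful curve could arise with no predictive value within either arm.

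**What to change.** 1. Reconcile Section 1.1, Section 7.1 footnote b and Section 7.4 so that all give one timing for the first thiamine sample, stated as before the first study infusion. The other baseline laboratory tests can keep their two-day window.
2. In Section 9.3, analyse the end-of-treatment level within arm or adjusted for arm, and do not derive a cutoff from a pooled curve alone.
3. Add the pre-dose level as a second predictor, with arm in the model and an exploratory arm interaction. With about 13 and 5 events at most, report these as estimates with intervals.
4. For patients already sampled, classify the first level as pre- or post-dose from recorded draw and infusion times, where these exist, before any analysis by outcome.
5. Minor: prefer day 8 or 9 for the end-of-treatment sample unless discharge comes first.

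Cost: no new assay, since the sample is already planned; an occasional draw separate from the routine Monday and Thursday bloods; and a little more analysis.

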	3	Significant cognitive deficits which are diffuse, i.e., affecting many different areas tested; must include periods of disorientation to time or place at least once each 24-hr period; registration and/or recall are abnormal; concentration is reduced
	4	Severe cognitive deficits, including motor or verbal perseverations, confabulations, disorientation to person, remote and recent memory deficits, and inability to cooperate with formal mental status testing

7. Physical disorder

	0	None present or active
	1	Presence of any physical disorder which might affect mental state
	2	Specific drug, infection, metabolic, central nervous system lesion, or other medical problem which can be temporally implicated in causing the altered behavior or mental status

8. Sleep-wake cycle disturbance

	0	Not present; awake and alert during the day, and sleeps without significant disruption at night
	1	Occasional drowsiness during day and mild sleep continuity disturbance at night; may have nightmares but can readily distinguish from reality

	2	Frequent napping and unable to sleep at night, constituting a significant disruption of or a reversal of the usual sleep-wake cycle
	3	Drowsiness prominent, difficulty staying alert during interview, loss of self-control over alertness and somnolence
	4	Drifts into stuporous or comatose periods

9. Lability of mood

	0	Not present; mood stable
	1	Affect/mood somewhat altered and changes over the course of hours; patient states that mood changes are not under self-control
	2	Significant mood changes which are inappropriate to situation, including fear, anger, or tearfulness; rapid shifts of emotion, even over several minutes
	3	Severe disinhibition of emotions, including temper outbursts, uncontrolled inappropriate laughter, or crying

10. Variability of symptoms

	0	Symptoms stable and mostly present during daytime
	2	Symptoms worsen at night
	4	Fluctuating intensity of symptoms, such that they wax and wane during a 24-hr period

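### Missed DRS ratings during acute illness, and in-hospital death, have no stated handling in the primary endpoint; read literally, the rules count some patients as non-delirious and replace others

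*Combined protocol and SAP*

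**What the plan says.** The primary endpoint (3.1, 9.1, 9.3) is any DRS > 12 between the day after transplant and day 30 or discharge, compared between arms by a chi-squared test.

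- **Rating schedule (7.4):** "The CRA(s) or investigators will continue to assess for delirium, using the DRS, three times weekly".
- **Exception (7.4):** "The DRS assessments will not be performed if a patient becomes unevaluable due to an acute medical concern (e.g. intubation, sedation, etc". No substitute rating is specified, and none is tied to recovery beyond the routine schedule.
- **Evaluability (7.11):** besides the dose criterion of 17/21, patients must "have delirium assessed at least weekly until one of the following is met". Three end events follow: "The participant is found to be delirious (DRS>12)", "The participant is at least 30 days post-transplant", and discharge. Death is not among them.
- **Consequence (7.11):** "If a patient is deemed not evaluable, they will be replaced by a new patient". A patient who becomes delirious during the intervention is kept.
- **Analysis population (9.1):** the 17/21 dose rule plus at least one delirium assessment weekly, with no end events.
- **Death elsewhere:** 5.7 names death as an end of follow-up, and 1.2 reports a 14-fold mortality rate with delirium in this population.

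Section 9.3 gives no rule for missed ratings or death in the primary comparison, no sensitivity analysis, and no analysis of all randomised patients.

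**The concern.** A single recorded DRS > 12 decides the endpoint, so what happens on unrated days matters. Intubation, sedation and death occur after randomisation, and the plan's own background ties delirium to mortality. Ratings lost to these events cannot be assumed unrelated to the outcome.

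The rules also treat the same kind of event differently according to its length. A short episode keeps the patient in the analysis as a negative. A long one removes the patient and brings in a replacement. With 30 patients per arm, one reclassified patient moves an arm by 1/30 = 3.3 percentage points. If handling is settled only after the data are seen, the primary result could depend on that choice.

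**Working it through.** **Step 1. Apply the rules to three patients with no recorded DRS > 12.**

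| Patient | 7.4 | 7.11 and 9.1 | Result |
|---|---|---|---|
| (a) Sedated for 5 days | No DRS in the gap | Weekly minimum still met | Evaluable; non-delirious unless a later rating exceeds 12 |
| (b) Unevaluable for more than a week | No DRS in the gap | Weekly minimum not met | Replaced |
| (c) Rated regularly, dies in hospital on day 20 | Ratings end at death | None of the three end events is reached | Can be read as non-evaluable and replaced |

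The outcomes for (a) and (c) are not stated in words. They follow from the binary endpoint and the three-item list. The plan does not say whether weekly means a calendar week or a rolling seven days, so the boundary between (a) and (b) is approximate.

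**Step 2. Reproduce the stated power (9.2).** Inputs: 0.445 v 0.155, n = 30 per arm, one-sided 0.05. The pooled proportion is 0.300.
- SE under the null: √(2 × 0.300 × 0.700/30) = 0.1183.
- SE under the alternative: √((0.445 × 0.555 + 0.155 × 0.845)/30) = 0.1122.
- z = (0.290 − 1.645 × 0.1183)/0.1122 = 0.850, giving power 0.802.

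The stated 80% reproduces. Exact binomial enumeration of the same uncorrected test gives 0.811, and that is the baseline below.

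**Step 3. Equal misses in both arms.** The documents give no rate of unevaluable periods or death. Assume a share h of true cases exceeds 12 only while unrated. If these cases are counted as non-delirious, the observed rate is p(1 − h). If they are replaced, it is p(1 − h)/(1 − ph).

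| h (assumed) | Counted non-delirious: rates | Difference | Exact power | Replaced: difference | Exact power |
|---|---|---|---|---|---|
| 0 | 0.445 v 0.155 | 0.290 | 0.811 | 0.290 | 0.811 |
| 10% | 0.401 v 0.140 | 0.261 | 0.762 | 0.277 | 0.798 |
| 15% | 0.378 v 0.132 | 0.246 | 0.735 | 0.270 | 0.789 |
| 25% | 0.334 v 0.116 | 0.217 | 0.676 | 0.255 | 0.769 |

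At h = 10% the expected number of affected patients is 30 × 0.445 × 0.10 = 1.3 in control and 30 × 0.155 × 0.10 = 0.5 on thiamine.

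**Step 4. Replacement can also widen the difference.** Suppose instead that the same share of patients, u = 10%, is replaced in each arm and that all of them were delirious. The rates become (0.445 − 0.10)/0.90 = 0.383 and (0.155 − 0.10)/0.90 = 0.061. The difference rises from 0.290 to 0.322.

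**Step 5. Unequal misses with no true effect.** Set both true rates to 0.445 and count missed cases as non-delirious. The exact one-sided rejection probability is:
- no misses: 0.046
- control 0%, thiamine 10%: 0.090
- control 10%, thiamine 0%: 0.021

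**The case against.** Several points on the other side stand.

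- **Not rating during sedation is defensible.** Section 5.9.1 describes the DRS as "using all available information from the patient interview, mental status examination, medical history and tests, nursing observations, and family reports", and Appendix B includes the level "Drifts into stuporous or comatose periods". A reader might infer that the scale should simply be completed throughout. But a patient sedated for a procedure could score 3 on item 1, 4 on item 6, 2 on item 7 and 4 on item 8. That is 3 + 4 + 2 + 4 = 13, above the cut-off, from sedation alone. Amendment 3 introduced the rule deliberately.
- **Ascertainment does not stop for good.** Three-times-weekly ratings run up to the event and apply again once the patient is evaluable, with a 24-hour look-back. Delirium that outlasts a short gap would probably be caught. Appendix A also routes behavioural disturbance to psychiatry, mostly to study investigators, although it mandates no DRS at that consult.
- **Replacement after death is not stated.** It is the literal reading of 7.11. Under 9.1, a patient rated every week until death arguably qualifies. The handling is therefore undefined.
- **The size is unknown.** No document figure supports a hidden share of 10% or 25%, and the replacement branch costs only about 1 to 4 points of power.
- **Part of this belongs to the evaluable-population rule.** Analysing all randomised patients would keep (b) and (c). It would not help (a), who is already in the analysis as a negative.

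**Conclusion.** The concern holds as a gap in how the primary endpoint handles unrated acute periods and in-hospital death. The written rules score some patients as non-delirious and remove others after randomisation because of events that the plan itself associates with delirium. It applies only to patients with no recorded DRS > 12 before the event or after recovery.

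A reader might infer that incidence is necessarily understated and the arm difference shrinks. The documents do not support that. Dilution follows if equal shares of cases are missed in both arms (at 10%, exact power 0.81 to 0.76). Replacement can widen the difference, and unequal misses can favour either arm (one-sided error 0.046 to 0.090, or to 0.021). All these figures rest on assumed shares and show sensitivity; they are not estimates of what will occur. The change should be made because it is cheap and because a missed recovery rating or an unlogged gap is hard to reconstruct later.

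**What to change.** **7.11 and 9.1.** Add death as an end of the weekly-assessment requirement, with the same end events in both sections. State that death, or a gap due to an acute medical event, does not make a patient non-evaluable or replaceable. Say how this interacts with the 17/21 dose criterion, which an early death or illness could also fail.

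**7.4.** Keep the rule of not rating during sedation or intubation. Require a DRS on the first evaluable study day after recovery, whatever the three-times-weekly schedule. Record the start, end and reason of each unevaluable period. Existing raters may add a chart-informed DRS for the 24 hours before the event, flagged and used only in a supportive analysis.

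**9.3.** Add sensitivity analyses of the primary endpoint for patients who died or had an unrated acute period without a DRS > 12. Count them as delirious in both arms, as non-delirious in both arms, and differently by arm in each direction. More than one scenario is needed because retention has a price. A long-gap case that no rating catches moves from replaced to counted non-delirious, which at a 10% hidden share is 0.798 to 0.762 in exact power.

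**Cost.** A protocol amendment, a small eCRF addition, and one or two ratings of up to 10 minutes (5.9.1) per affected patient. Chart-informed ratings are less certain than interviews, which is why they stay supportive.
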